### LIST OF ABBREVIATIONS

Abbreviation	Term
PP	Per Protocol
PT	Prothrombin Time
PTT	Activated Partial Thromboplastin Time
RBC	Red Blood Cell
SAE	Serious Adverse Event
SAP	Statistical Analysis Plan
SAS	Statistical Analysis System
SD	Standard Deviation
SF-36	36-Item Short-Form Questionnaire
TEAE	Treatment-Emergent Adverse Event
UC	Ulcerative Colitis
UCDAI	Ulcerative Colitis Disease Activity Index
USP	United States Pharmacopeia
WBC	White Blood Cell
WHO-DD	World Health Organization Drug Dictionary

## 1. INTRODUCTION

The purpose of this document is to provide details about the statistical analysis methods specified in the study protocol IBD98-M-2002: A Phase 2a, Multicenter, Randomized, Double-blind, Parallel-group, Placebo-controlled Trial of IBD98-M Delayed-release Capsules to Induce Remission in Patients with Active, Mild to Moderate Ulcerative Colitis, sponsored by Holy Stone Healthcare Co., Ltd. This Statistical Analysis Plan (SAP) is based on the Protocol Amendment 3 dated 09 May 2017.

## 2. STUDY OBJECTIVES

### Primary

To compare the percentage of patients in ulcerative colitis (UC) remission at Week 6 for each of the two IBD98-M dose groups versus placebo (remission defined as the modified Ulcerative Colitis Disease Activity Index [UCDAI] score of  $\leq 1$ , with a score of 0 for rectal bleeding and stool frequency, no mucosal friability, and sigmoidoscopy score not exceeding 1).

### Secondary

- To compare clinical improvement rates at Week 6 among treatment groups (defined as a  $\geq 3$  point reduction from baseline in the modified UCDAI score)
- To compare endoscopic improvement at Week 6 among treatment groups (defined as a  $\geq 1$  point decrease from baseline in modified UCDAI mucosal appearance subscore)
- To determine the change in symptoms (rectal bleeding and stool frequency) from baseline to each study visit among treatment groups
- To evaluate the safety and tolerability profile of IBD98-M

### Exploratory

- To examine the effect of IBD98-M treatment on fecal calprotectin
- To examine any correlation between therapeutic response to IBD98-M and baseline characteristics

### 3. STUDY DESIGN AND PLAN

Study IBD98-M-2002 is a Phase 2a, multicenter, randomized, double-blind, parallel group, placebo-controlled trial in patients with active, mild to moderate UC. It is being conducted as an exploratory proof-of-concept study to investigate the clinical efficacy of IBD98-M delayed-release capsules (in a fixed combination) over a 6-week treatment period and a 2-week follow-up period.

Patients will be screened for study enrollment up to 2 weeks prior to randomization (Visit 3). During the screening period, patients will be evaluated with laboratory tests, physical examinations, and sigmoidoscopy. To be eligible, patients are to have a score of  $\geq 4$  and  $\leq 10$  on the modified UCDAI, and a score of  $> 1$  on the endoscopy subscore would be included. In addition, the diagnosis of UC must be confirmed visually by endoscopy images and also by histologic evidence in the past. After the screening visits, eligible patients will be randomized to 1 of 3 study groups:

- (1) IBD98-M 0.8 g/day (mesalamine 0.8 g with sodium hyaluronate 92 mg),
- (2) IBD98 M 1.2 g/day (mesalamine 1.2 g with sodium hyaluronate 138 mg), or
- (3) Placebo.

Up to 51 patients will be enrolled in this study (including drop-out patients), with 17 patients randomized to each treatment group. Study blind will be maintained using a double-dummy technique.

Eligible patients will be randomized centrally via an Interactive Web Response System (IWRS), and each patient will receive 3 capsules twice a day (BID) for a period of 6 weeks, administered orally in 1 of the following regimens:

- Patients in the 0.8 g/day group will receive 2 capsules of IBD98-M (200 mg of mesalamine/23 mg of sodium hyaluronate) and 1 placebo capsule BID.
- Patients in the 1.2 g/day group will receive 3 capsules of IBD98-M (200 mg of mesalamine/23 mg of sodium hyaluronate) BID.
- Patients in the placebo group will receive 3 placebo capsules BID.

Patients should be encouraged to take their medication at the same time 30-120 minutes before meals every day. During the study, patients will visit the clinic on 7 occasions: 2 visits during the screening period (the second screening visit is the baseline visit); 4 visits during the treatment period at weeks 0, 2, 4, and 6; and an end-of-study/withdrawal visit at week 8, concluding the follow-up period. Patients will record symptoms in a daily diary starting 7 days before treatment and continuing until the end-of treatment period (Visit 6). For the baseline scoring of rectal bleeding and stool frequency items, the worst score from the previous 7 days of diary data before the randomization visit will be used excluding the day of and the day after endoscopy, as well bowel preparation for endoscopy where applicable.

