#### Timing of diary entries for UCDAI

- At Baseline (Day 0), the timing of the diary entries depends on when the endoscopy is performed
  - If the endoscopy is performed within 5 days of randomization (Day 0), use the diary entries from 3 consecutive days immediately prior to the preparation day for the endoscopy.
  - If the endoscopy is performed 6 to 14 days prior to the randomization day (Day 0), the diary entries from 3 consecutive days immediately prior to Day 0 should be used.
  - The endoscopy must be performed within 14 days of randomization (Day 0).
- For visits where an endoscopy is not needed (Day 14 and 28), diary entries from the 3 days preceding the visit day will be used for the assessment of stool frequency, rectal bleeding, and physician's global assessment.
- For the Day 42 visit, diary entries from the 3 days preceding the visit day or the preparation for endoscopy, whichever comes first, will be used for the UCDAI assessment. Endoscopy must be performed within 3 days of the target visit day.

See Appendix 1 for further detail.

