### **12 STATISTICAL ANALYSIS**

A Statistical Analysis Plan (SAP) will be prepared after the protocol is approved. This document will provide further details regarding the definition of analysis variables and analysis methodology to address all study objectives. The SAP supersedes the protocol's analysis sections in case of differences.

The statistical evaluation will be performed using Statistical Analysis Software (SAS®) Version 9.2 or higher (SAS Institute, Cary, NC). All data will be listed, and summary tables will be provided. Summary statistics will be presented by treatment group. For continuous variables, data will be summarized with the number of patients,

mean, standard deviation, median, minimum, and maximum by treatment group. For categorical variables, data will be tabulated with the number and percentage of patients for each category by treatment group.

One interim analysis is planned.

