#### 5. DEFINITIONS AND DERIVED VARIABLES

Study Start Date, Study Stop Date, and Duration: Study start date for a given patient is defined as the date of screening and study stop date is defined as the date on which the patient end of study form was completed at the end of study. Study duration is defined as (study stop date – study start date) + 1 in days.

Baseline: Baseline for all safety and efficacy measurements will be defined as the last assessment prior to study drug administration unless stated otherwise.

Study Day: Study day will be calculated by subtracting date of first dose date i.e. day 1 from respective event date. Day 1 is the date of the first dose of study drug.

Study day= Event date – Day 1 date.

Study day= Event date – Day 1 date + 1 (For those events occurring on or after Day 1).

Modified UCDAI Score: The modified UCDAI score will be computed as combined score of stool frequency, rectal bleeding, mucosal appearance, and the physician's global assessment.

Sigmoidoscopy Score: It is the “mucosal appearance” score which is collected at visit 3 and 6 along with Rectal Bleeding, Stool Frequency and Physicians Global Assessment.

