#### Proportion of Patients With Clinical Improvement at Week 6:

The modified UCDAI score system includes four variables, namely rectal bleeding, stool frequency, mucosal appearance, and the physician's global assessment of disease activity. Each variable is scored from 0 – 3 so that the total score (a summation of the 4 variable scores) ranges from 0 – 12, with higher scores indicating more severe disease.

A patient will have experienced clinical improvement at Week 6 if the change from baseline (the last assessment prior to the first dose of study drug) to Week 6 (Visit 6) in the modified UCDAI score is  $\leq -3$ , where change is computed as the Week 6 modified UCDAI score minus the baseline modified UCDAI score. Only patients with a modified UCDAI score at baseline and Week 6 will have their clinical improvement status determined (no non-responder imputation).

The proportion of patients with clinical improvement at Week 6 will be summarized and analyzed using methodology similar to the primary efficacy endpoint for both the ITT and PP populations. A bar chart of the percentage of patients with clinical improvement at Week 6 by treatment group will be presented.

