#### Proportion of Patients With Endoscopic Improvement at Week 6:

A patient will have experienced endoscopic improvement at Week 6 if the change from baseline (the last assessment prior to the first dose of study drug) to Week 6 (Visit 6) in the modified UCDAI mucosal appearance score is  $\leq -1$ , where change is computed as the Week 6 score minus the baseline score.

Missing data will not be imputed at Week 6 if a patient has not made it to Week 6 and/or has no Week 6 mucosal appearance result.

The proportion of patients with endoscopic improvement at Week 6 will be summarized and analyzed using methodology similar to the primary efficacy endpoint for both the ITT and PP populations. A bar chart of percentage of patients with endoscopic improvement at Week 6 by treatment group will be presented.

Change in Symptoms (Rectal Bleeding and Stool Frequency) From Baseline to Each Study Visit:

Rectal bleeding is scored at each visit as normal (none), mild (streaks of blood), moderate (obvious blood), or severe (mostly blood). Stool frequency is scored at each visit as normal (none), mild (1-2 stools more than usual per day), moderate (3-4 stools more than usual per day), or severe ( $>4$  stools more than usual per day).

The number and percentage of patients with each categorical result will be presented for each symptom (rectal bleeding and stool frequency) at baseline (the last assessment prior to the first dose of study drug) and each post baseline visit for ITT and PP populations. Each IBD98-M group will be compared to placebo at each visit using Fisher's exact test.

A shift table will be prepared for each symptom, showing the number and percentage of patients with normal, mild, moderate, and severe results at baseline versus normal, mild, moderate, and severe results at each post-baseline visit, by treatment group.

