## 17. APPENDIX

### 17.1 Modified Ulcerative Colitis-Disease Activity Index Scoring System

	Mild (score = 1)	Moderate (score = 2)	Severe (score = 3)
Rectal bleeding	Streaks of blood	Obvious blood	Mostly blood
Stool frequency	1-2/day > normal	3-4/day > normal	>4/day > normal
Mucosal appearance	Erythema Decreased vascular pattern Minimal granularity	Marked erythema Friability Granularity Absent vascular pattern Bleeding minimal trauma No ulcerations	Ulceration Spontaneous bleeding
Physician's Global Assessment	Mild	Moderate	Severe

Note: Normal = 0

Modified from Sutherland et al. (Mucosal friability moved from a score of 1 to 2).

Note: In those cases, when patients have variable values for one or more modified UCDAI items, the average must be calculated.

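### Baseline bleeding and stool scores have conflicting diary rules; pairing worst-of-7-days at baseline with 3 days at follow-up would inflate absolute clinical improvement rates and symptom shifts in every arm

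*SAP*

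**What the plan says.** Three rules bear on the two diary-based UCDAI items.

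- **Worst of 7 days.** SAP 3 and Protocol 6.1 both say that for baseline "the worst score from the previous 7 days of diary data before the randomization visit will be used", leaving out bowel preparation, the endoscopy day and the day after.
- **Three days.** Protocol 10.1 covers the same baseline items. If endoscopy falls within 5 days of randomization, sites are to "use the diary entries from 3 consecutive days immediately prior to the preparation day for the endoscopy". If it falls 6 to 14 days before, the 3 days before Day 0 apply. At Days 14 and 28, "diary entries from the 3 days preceding the visit day will be used for the assessment of stool frequency" and the other partial-score items. Day 42 also uses 3 days, before the visit or the endoscopy preparation, whichever is earlier.
- **Average.** A note in SAP 17.1 says that "when patients have variable values for one or more modified UCDAI items, the average must be calculated". It names no visit, window or rounding rule.

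SAP 5 adds: "Baseline for all safety and efficacy measurements will be defined as the last assessment prior to study drug administration unless stated otherwise". For clinical improvement, SAP 7.8.2 takes the "change from baseline (the last assessment prior to the first dose of study drug) to Week 6 (Visit 6) in the modified UCDAI score" and requires a fall of at least 3 points. For symptoms, its shift tables show "patients with normal, mild, moderate, and severe results at baseline versus normal, mild, moderate, and severe results at each post-baseline visit".

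The SAP gives no scoring window for follow-up diaries. SAP 7.8.1 and Protocol 12.4.1 do name a diary period, Day 36 to study end, but it only decides who counts as a non-responder on the primary endpoint.

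**The concern.** A programmer cannot apply all three rules at once, and the choice is not neutral. The worst of several days sits above the average of a few days. Scoring baseline the first way and follow-up the second builds in a fall that owes nothing to treatment or disease course.

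Two outputs carry it: the absolute rate of clinical improvement (a secondary endpoint) and the symptom shift tables. With 17 patients per arm in a proof-of-concept trial, readers will look at those absolute figures directly. There is also a practical gap: an average of daily scores need not be a whole number, so it does not fit the normal/mild/moderate/severe tables without a rounding rule.

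**Working it through.** **1. Do the documents settle the rule?** No.

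- Protocol 12 states: "The SAP supersedes the protocol's analysis sections in case of differences". This does not help, because the SAP itself contains both worst (section 3) and average (17.1).
- The baseline definitions in SAP 5 and 7.8.2 fix the assessment, not the diary days behind it.
- One reading removes the conflict inside the SAP: worst at baseline, average afterwards. That is the mismatched pairing.

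**2. Direction, by hand.** Assume an item scores 1 or 2 with probability 1/2 each day, independently, with no true change.

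- Expected worst of k days = 2 − (1/2)^k: 1.875 for k = 3, 1.9375 for k = 4, 1.992 for k = 7.
- Expected 3-day mean = 1.5.
- Baseline worst of 4: the item falls by 1.9375 − 1.5 = 0.44 against a 3-day mean, or 1.9375 − 1.875 = 0.06 against worst of 3.
- Baseline worst of 7: the item falls by 0.49 or 0.12.

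The sign holds for any day-to-day variation once baseline has 4 or more usable days. Only the size depends on assumptions.

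**3. Usable baseline days.** SAP Table 1 places sigmoidoscopy on Day -7 to -1. With one preparation day (assumed) and randomization on Day 0:

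- endoscopy on Day -7 or -1 leaves 5 of the 7 days;
- endoscopy on Day -6 to -2 leaves 4.

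Visit 3 may move by ±3 days. Endoscopy on Day -7 with randomization on Day +2 makes the window Day -5 to +1, and all 7 days are usable.

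**4. Illustrative size.** The plan states no figure for this, so there is none to reproduce. Simulation of 400,000 patients per scenario, all inputs assumed:

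- two items, patient mean 1.5 (SD 0.6), daily score rounded and clipped to 0–3;
- day-to-day SD 0.3 to 0.7, adjacent-day correlation 0 to 0.5;
- 4 or 5 usable baseline days, endoscopy and physician items held fixed, no true change.

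| Follow-up score | False 3-point fall, worst-of-usable-days baseline | Same 3-day rule at both times |
|---|---|---|
| 3-day mean, unrounded | up to 7.5% | up to 0.4% |
| 3-day mean, rounded | up to 14.7% | up to 1.7% |
| Worst of 3 days | up to 3.5% | up to 2.0% |

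Per arm of 17, the maxima are 0.075 × 17 = 1.3, 0.147 × 17 = 2.5 and 0.035 × 17 = 0.6 patients. The mean two-item fall is 0.5 to 1.5 points (unrounded mean) or 0.1 to 0.4 (worst of 3). It is zero under a matched rule.

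Shift table, one symptom:

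| Follow-up score | Better | Worse |
|---|---|---|
| Rounded 3-day mean | 29–65% | 1–10% |
| Worst of 3 days | 15–35% | 8–22% |
| Matched 3-day rule | 11–27% | 11–27% |

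With all 7 baseline days usable, false falls reach 10.7% (unrounded mean) or 5.0% (worst of 3).

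**5. What is untouched.** SAP-defined remission uses Week 6 scores only. Endoscopic improvement uses the mucosal score only. The post-baseline Fisher tests of symptom categories compare arms at a visit without reference to baseline.

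**The case against.** **The pairing is not prescribed.** It joins a SAP sentence to Protocol 10.1, and the SAP rests on Protocol Amendment 3, dated 09 May 2017. The supplied protocol may be another version: the SAP cites a Protocol Section 7.4 that it lacks, starts screening at Day -14 rather than -28, and plans no interim analysis where the protocol plans one. Amendment 3 may contain a matching follow-up rule. This stands, and it makes the bias conditional. It does not remove the clash between Protocol 6.1 and 10.1, or between worst and average inside the SAP.

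**The SAP has a Week 6 diary period.** Day 36 to study end might be taken for a scoring window. It decides only whether data exist, but it should be checked for consistency with whatever rule is adopted.

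**Scores may be set at the visit.** SAP 7.8.2 describes each symptom as scored at each visit, and SAP 5 describes item scores as collected at Visits 3 and 6. If only visit-level scores reached the database, new wording cannot rescore anyone. This stands and affects the remedy.

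**The effect is modest.** All arms share the rule, including placebo. A reader might infer that the treatment comparison or the primary result is biased. The documents do not support that: with no treatment effect the drift is equal across arms, and SAP-defined remission uses no baseline symptom score.

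**Conclusion.** The conflict is real and unresolved in the supplied documents. If worst-of-7 at baseline is combined with 3-day follow-up, absolute clinical improvement rates and symptom shift tables are biased towards improvement in every arm whenever daily scores vary. The direction is arithmetic; the size is unknown.

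The percentages above are illustrations, not bounds. In particular, 7.5% should not be read as a ceiling: it needs an unrounded mean and 4 or 5 usable days, and rounding roughly doubles it. The low matched-rule figures also rest on holding the other two items fixed. A separate set of runs, with assumed retest noise (SD 0.4) in those items and day-to-day SD 0.3 to 0.8, gave 1.5% to 4.8% under a matched 3-day rule.

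No false between-arm difference follows. This is a low-end fix to one secondary rate and some descriptive tables.

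**What to change.** Before unblinding, reconcile Protocol 6.1 and 10.1 with SAP 3 and 17.1, check Protocol 12.4.1 and SAP 7.8.1 for consistency, and confirm the wording against Protocol Amendment 3. State, for baseline and every follow-up visit:

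- one window length (either will do if it is the same throughout; 3 days is the only one the supplied documents already define for all visits);
- one summary, mean or worst; if worst, also a fixed number of usable days;
- one rounding rule to the 0–3 categories;
- a fallback for missing diary days.

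State that the reconciled score is for analysis only and does not reopen entry decisions. Rescoring could otherwise put an enrolled patient below the UCDAI minimum of 4 (with an endoscopy score of at least 2, the other three items would have to sum to less than 2), and SAP 7.2 counts a failed entry criterion as a major deviation.

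Confirm that daily diary entries are in the database. If only visit-level scores were collected, report the absolute improvement rates and shift tables with the mismatch stated as a limitation.

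**Cost:** wording in both documents, possibly lower reported improvement rates, and reprogramming if daily data exist. The fallback matters. With one preparation day and endoscopy on Day -4, the Protocol 10.1 baseline days are Days -8 to -6, while Protocol 6.1 and SAP 3 start the diary 7 days before treatment.

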### **3.1 Study Treatments and Assessments**

IBD98-M (mesalamine, United States Pharmacopeia [USP]; and sodium hyaluronate) drug product is a delayed-release capsule. Each capsule is filled with multiple-layer pellets containing 200 mg of mesalamine and 23 mg of sodium hyaluronate. Each pellet consists of a microcrystalline cellulose inner core, which is coated first with mesalamine, USP; then with sodium hyaluronate, and finished with an enteric coating film.

The enteric-coated pellets are designed to allow the release of mesalamine and sodium hyaluronate from the pellets at or above pH 6.8 at the terminal ileum (ascending colon).

The matching placebo capsule will be indistinguishable from the drug capsule. The capsules (placebo or drug) are packaged, 35 count per bottle, into 60-cc white, wide-mouth, round HDPE (High Density Polyethylene) bottles sealed with an aluminum foil pad and covered with a polypropylene plastic cap. The product stability is for 24 months when the product is stored in a stability chamber of 25° C +/- 2° C. The product should be stored at 15° to 25° C [59° to 77° F].

**Details of Study Medications:**

	Preparations to be Administered		
	Placebo	Test Product (New Drug)- 0.8 g/day dose group	Test Product (New Drug)- 1.2 g/day dose group
Investigational Name	Not applicable	IBD98-M	IBD98-M
Manufacturer	Holy Stone Healthcare	Holy Stone Healthcare	Holy Stone Healthcare
Total Daily Dose	Not Applicable	Mesalamine 0.8 g; sodium hyaluronate 92 mg (total 4 capsules)	Mesalamine 1.2 g; sodium hyaluronate 138 mg (total 6 capsules)
Dosage	3 placebo capsules, BID	2 test product capsules and 1 placebo capsule, BID	3 test product capsules BID
Route	Oral	Oral	Oral
Formulation	Capsule	Capsule	Capsule
Capsule Strength	Not Applicable	Mesalamine 200 mg; sodium hyaluronate 23 mg	Mesalamine 200 mg; sodium hyaluronate 23 mg

**Table 1: Schedule of Events**

STUDY PROCEDURE	Screening*			Treatment Period			Follow-up	
	Visit 1 (Screening)	Visit 2 (Baseline)	Visit 3	Visit 4	Visit 5	Visit 6/Early termination	Visit 7	
DAY	-14 to -7	-7 to -1	0 ( $\pm$ 3)	14 ( $\pm$ 3)	28 ( $\pm$ 3)	42 ( $\pm$ 3)	56 ( $\pm$ 3)	
Informed consent	X							
Demographics/Medical History	X							
Confirm Study Eligibility	X	X	X					
Vital Signs	X	X	X	X	X	X	X	
Physical Examination	X	X	X	X	X a	X a	X	
Weight, Height, and BMI	X	X						
12-Lead ECG	X							
Hepatitis Screening b	X							
CBC with Differential	X		X	X	X	X	X	
Coagulation (aPTT, PT, INR)	X			X	X	X	X	
Serum Chemistry c	X			X c	X	X c	X c	
Urinalysis	X			X	X	X	X	
Pregnancy Test d	X			X	X	X	X	
Adverse Events	X		X	X	X	X	X	
Concomitant Medications	X		X	X	X	X	X	
Modified UCDAI e	X		X	X	X	X	X	
IBDQ, SF-36			X					
CRP			X					
Flexible Sigmoidoscopy		X f						
Distribution of Diary/Check	X	X	X	X	X	X	X	
Stool for culture, C. difficile toxin, and ova and parasite h		X						
Randomization			X g					
Treatment Distribution/accountability j			X	X	X	X	X	
Stool Calprotectin			X					

Abbreviations: BMI= body mass index; ECG= electrocardiogram; CBC= complete blood count; aPTT= activated partial prothrombin time; PT= prothrombin time; INR= international normalization ratio; UCDAI= Ulcerative Colitis Disease Activity Index; IBDQ= Inflammatory Bowel Disease Questionnaire; SF-36= 36-Item Short Form Questionnaire; CRP= C-reactive protein; *C. difficile*= *Clostridium difficile*; AE= adverse event; HIV= human immunodeficiency virus.

\*A patient who is screened and does not meet the study entry criteria may be re-screened again only once. Please refer to Protocol Section 7.4 (Re-screening) for further details.

- a. Physical examinations performed on Days 14 and 28 will be abbreviated physical examinations. New findings will be recorded as AEs.
- b. Blood samples will be collected for Hepatitis B and C screening; HIV testing will not be performed in this study.
- c. Cholesterol and triglycerides assessments will be done at Visits 3 and 6 only.
- d. Pregnancy test performed at screening should be serum test, after screening should be urine pregnancy tests. All pregnancy test results must be available before patient dosing.
- e. Modified UCDAI on Days 0 and 42 should be complete modified UCDAI score including the endoscopy subscore. Modified UCDAI at Screening Visit 2, Visit 4, and Visit 5 should be partial modified UCDAI score including only stool frequency, rectal bleeding and physician's global assessment.
- f. Screening sigmoidoscopy must be performed on Day -7 to Day -1.
- g. No distribution of diary at Visit 6. Only check diary from Visit 5
- h. A sample will be collected and cultured during screening and at any point in the study when a patient becomes symptomatic, including worsening or return of disease activity.
- i. To be performed prior to dosing.
- j. Treatment distribution will be done at Visits 3, 4, and 5. Treatment accountability will be done at Visits 4, 5, and 6. All unused medication is to be returned at Visits 4, 5, and 6.

